3.7 Other Additional Analyses

3.7.1 Immunology Profile

The ANA and extractable nuclear antigen (ENA) (RNP, Sm, SSA, SSB) results will be summarized by visit for the subjects with abnormal value at baseline. The shift from baseline in ANA and ENA will be summarized by visit.

The quantitative immunoglobulins levels as well as their changes from baseline will be summarized by visit.

3.8 Safety Analyses

3.8.1 Adverse Events and Serious Adverse Events

Adverse events (AEs) will be coded by MedDRA version 18.0 or higher and the type incidence, severity and relationship to study investigational product will be summarized. Specific adverse events will be counted once for each subject for calculating percentages. In addition, if the same AE occurs multiple times within a particular subject, the highest severity and level of relationship observed will be reported. All treatment-emergent AEs will

be summarized overall, as well as categorized by MedDRA System Organ Class and Preferred Term.

The acute AEs are defined as events that occur within a 24 hour period after dosing. The acute AEs will be summarized.

The treatment-emergent non-serious AEs will also be summarized.

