An AE includes but is not limited to any clinically significant worsening of a subject's pre-existing condition. An abnormal laboratory finding (including ECG finding) that requires an action or intervention by the investigator, or a finding judged by the investigator to represent a change beyond the range of normal physiologic fluctuation, should be reported as an AE. The worsening and/or flare of SLE disease activity will be captured in the disease activity assessments or other study-specific CRFs (ie, SLE Increase in Disease Activity CRF), and not recorded as an AE, unless it meets the definition for an SAE or AESI. If clinical sequelae are associated with a laboratory abnormality, the diagnosis or medical condition should be reported (eg, renal failure, hematuria) not the laboratory abnormality (eg, elevated creatinine, urine RBC increased). Abnormal laboratory values that are not, in the investigator's opinion, medically significant and do not require intervention should not be reported as AEs.

Adverse events may be treatment emergent (ie, occurring after initial receipt of investigational product) or nontreatment emergent. A nontreatment-emergent AE is any new sign or symptom, disease, or other untoward medical event that begins after written informed consent has been obtained but before the subject has received investigational product.

Elective treatment or surgery or preplanned treatment or surgery (that was scheduled prior to the subject being enrolled into the study) for a documented pre-existing condition that did not worsen from baseline is not considered an AE (serious or nonserious). An untoward medical event occurring during the prescheduled elective procedure or routinely scheduled treatment should be recorded as an AE or SAE.

Nonserious AEs will only be captured during the first year of subject's participation in the study; however, nonserious AEs that result in interruption of investigational product and/or discontinuation from the study will be captured at any time during the subject's participation in the study. Serious adverse events and AESIs will be captured throughout the entire study participation.

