3.8.4 Exposure Adjusted Adverse Events Rate

The exposure adjusted rate (per 100 patient-year) for treatment emergent AEs, non-serious AEs, acute AEs, investigational product related AEs, AEs by highest severity, AEs leading to treatment discontinuation, AEs resulting in death, SAEs and AESIs will be summarized. The exposure adjusted subject rate per 100 patient-years is defined as [the number of subjects with an event/(total exposure time in days/365.25)]*100.

For treatment emergent AEs leading to treatment discontinuation, AEs resulting in death, SAEs and AESIs, duration of exposure is calculated as follows:

- Anifrolumab Total group: duration of exposure (days) = minimum(end of study date in CD1145, last dosing date in CD1145+85 days) – first dosing date in CD1145+1.

- Anifrolumab 1000 mg group:
 - For subjects who received 1000 mg only during the study: duration of exposure (days) = minimum(end of study date in CD1145, last dosing date in CD1145+85 days) – first dosing date in CD1145+1.
 - For subjects who received both 1000 mg and 300 mg during the study: duration of exposure (days) = (first dosing date of 300 mg – 1) – first dosing date in CD1145 + 1.
- Anifrolumab 300 mg group: duration of exposure (days) = minimum(end of study date in CD1145, last dosing date in CD1145+85 days) – first dosing date of 300 mg +1.

The AEs leading to treatment discontinuation, AEs resulting in death, SAEs and AESIs occurred during the exposure period will be included in the summary.

The non-serious AEs are captured during the first year of subject's participation only. So for treatment emergent AEs, non-serious AEs, acute AEs, investigational product related AEs, and AEs by highest severity, duration of exposure is calculated as follows:

- Anifrolumab Total group: duration of exposure (days) = minimum(end of study date in CD1145, first dosing date in CD1145+364) – first dosing date in CD1145+1.
- Anifrolumab 1000 mg group:
 - For subjects who received 1000 mg only during the study: duration of exposure (days) = minimum(end of study date in CD1145, first dosing date in CD1145+364) – first dosing date in CD1145+1.
 - For subjects who received both 1000 mg and 300 mg during the study: duration of exposure (days) = minimum(first dosing date in CD1145+364, first dosing date of 300 mg-1) – first dosing date in CD1145 + 1.
- Anifrolumab 300 mg group: minimum(end of study date in CD1145, first dosing date in CD1145+364) - first dosing date of 300 mg +1.

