The events occurred during the exposure period will be included in the summary.

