3.8.7 Subgroup Analyses

The treatment emergent AEs and SAEs will be summarized by 4-gene IFN signature (IFN high vs IFN low) and ADA status (positive vs negative).

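### SAP 3.8.1 sets no end date for its adverse event percentages, so the SOC/PT tables combine terms captured for one year with terms captured for up to 3.2 years

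*SAP*

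**What the plan says.** **Percentages.** SAP 3.8.1 counts each specific event once per subject and expresses it as a percentage. All treatment-emergent AEs will "be summarized overall, as well as categorized by MedDRA System Organ Class and Preferred Term", and severity and relationship are summarised. It adds: "The acute AEs will be summarized" and "The treatment-emergent non-serious AEs will also be summarized". No end date is given for any of these. SAP 3.8.7 repeats the TEAE and SAE summaries by IFN signature and ADA status, also without a period.

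**Treatment-emergent.** The SAP has no definition of its own. Protocol 6.1.1 gives a start but no end: "Adverse events may be treatment emergent (ie, occurring after initial receipt of investigational product) or nontreatment emergent".

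**Capture.** Protocol 6.1.1 and 6.1.3 collect SAEs and AESIs (serious or not) throughout participation. Other non-serious AEs are collected in the first year only, unless they lead to interruption of product or discontinuation from the study.

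**Rates.** SAP 3.8.4 recognises the limit: "The non-serious AEs are captured during the first year of subject's participation only". It then states that "for treatment emergent AEs, non-serious AEs, acute AEs, investigational product related AEs, and AEs by highest severity, duration of exposure is calculated as follows", and the formulas end the window no later than first dose+364. It closes the numerator to match: "The events occurred during the exposure period will be included in the summary". Discontinuation AEs, deaths, SAEs and AESIs run to the earlier of end of study and last dose+85 days.

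**The concern.** A percentage of subjects with an event depends on how long events are collected. With no cut, a term that is always serious or always an AESI accumulates over the whole study, while a term that is nearly always non-serious stops accumulating after a year. Both stand in the same SOC/PT table over the same denominator. A single preferred term can also be mixed internally, with serious occurrences counted throughout and non-serious ones counted only in year 1.

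Protocol 7.3.1 makes the TEAE and TESAE summaries the main assessment of the primary objective, with no formal testing. The descriptive tables are therefore the result. A reader would see serious and AESI terms as more frequent, relative to other non-serious terms, than they are. A reader setting the percentage for a category beside its exposure-adjusted rate would be comparing two different event counts.

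**Working it through.** **Windows, from the SAP 3.8.4 formulas**

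- Year-1 window: first dose to first dose+364 = 365 days.
- Full window for a completer, last dose at Week 156: 156×7 + 85 + 1 = 1092 + 85 + 1 = 1178 days. This agrees with Protocol 3.2: 156 + 12 = 168 weeks, and (1092 + 85)/7 = 168.1 weeks.
- Selective-capture time: 1178 − 365 = 813 days (2.23 years), which is 813/1178 = 69% of the full window. Ratio of windows: 1178/365 = 3.23.

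**Effect on one preferred term**

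The plan states no AE or discontinuation rates, so those below are assumed. For a term with true rate r per year, of which a fraction s stays captured after year 1, a completer's expected percentage is

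1 − exp(−r × (365 + s×813)/365.25).

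At r = 0.10:

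| Fraction still captured, s | Days in exponent | Percentage | Always-captured term (27.6%) relative to this term |
|---|---|---|---|
| 0 | 365 | 9.5% | 2.9 |
| 0.05 | 405.65 | 10.5% | 2.6 |
| 0.10 | 446.3 | 11.5% | 2.4 |
| 0.20 | 527.6 | 13.5% | 2.05 |
| 0.50 | 771.5 | 19.0% | 1.4 |
| 1 | 1178 | 27.6% | 1 |

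The row s = 0 ignores the interruption/discontinuation exception, so 2.9 is the upper endpoint at this rate. The rows 0.05 to 0.20 allow for it. A half-serious term against a term with s = 0.10 gives 19.0/11.5 = 1.7. The endpoint ratio itself varies with r: 3.2 at 0.02 and 2.4 at 0.30.

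**With discontinuation**

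Assume 20% per year at a constant hazard of −ln(0.8) = 0.223, with 85 days of follow-up after the last dose. Averaging the same expression over simulated last-dose times capped at day 1092 gives 21.1% for s = 1, and 9.6%, 10.3% and 11.6% for s = 0.05, 0.10 and 0.20. The ratios are 2.2, 2.05 and 1.8. The half-serious term shows 15.3%, so its ratio to s = 0.10 is 1.5.

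**Effect on the any-TEAE percentage, completer**

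With n non-serious AEs (no late capture) and m serious AEs per year:

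- with the cut: 1 − exp(−(n + m)×365/365.25)
- without the cut: 1 − exp(−(n + m)×365/365.25 − m×813/365.25)

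Results:

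- n = 2.0, m = 0.10: 87.7% against 90.2%, a rise of 2.4 points before rounding.
- n = 3, m = 0.05: 95.2% against 95.7%, a rise of 0.5 points.
- n = 1, m = 0.20: 69.9% against 80.7%, a rise of 10.8 points.

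These are the middle and extremes of a grid over n = 1 to 3 and m = 0.05 to 0.20. The range belongs to that grid and is not a bound.

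**The case against.** **The rates already handle it.** SAP 3.8.4 gives period-matched rates for every category at issue, and AESIs, deaths and discontinuation AEs have their own summaries. This largely stands: the rates are sound and no event is lost. But 3.8.4 names overall categories and does not mention SOC or PT, so it does not repair the SOC/PT percentages.

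**The programming plan may contain the cut.** SAP 1 assigns table templates and specifications to a separate document that is not available here, so a filter there cannot be excluded. The SAP refers visit windows to that document (3.1.1) but not the AE period. What is certain is that the SAP states no cut, not that the final tables will lack one.

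**Low consequence.** There is one treatment column (SAP 3.2.2) and no test. The harm arises only when a reader compares terms within a table or a percentage with a rate. That limits the weight of the point but does not remove it.

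A reader might also infer stronger readings that the documents do not support:

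- **A general threefold distortion.** This requires no late capture at all of non-serious events, and Protocol 6.1.1 keeps those causing interruption or discontinuation.
- **Acute AEs lost at 26 of 40 doses.** A completer does have 26 of 40 scheduled doses after first dose+364. But Protocol 4.5.6.1 makes reactions within 24 hours that are felt to be related to the infusion infusion reactions, and these are AESIs captured throughout. The uncaptured share is unknown.
- **Invalid subgroup contrasts in 3.8.7.** Both levels of each subgroup share one capture rule, so contrasts are affected mainly if retention differs. Levels and term rankings within a subgroup are affected as in 3.8.1.
- **A known shift in the severity distribution.** Protocol 6.2.1 separates seriousness from grade, and their overlap is not given.

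**Conclusion.** The point holds as a defect of consistency within the SAP. Section 3.8.4 recognises selective capture after year 1 and cuts for it; 3.8.1 and the TEAE tables in 3.8.7 summarise the same categories without the cut. Under the assumed rate of 0.10 per year, terms with equal true rates can differ about twofold in the SOC/PT table: 2.05 to 2.6 in a completer and 1.8 to 2.2 with 20% annual discontinuation, if 5% to 20% of the non-serious events stay captured. The any-TEAE percentage rises by 0.5 to 10.8 points over the completer grid. All these sizes rest on assumed event and discontinuation rates and a constant hazard; the windows of 365 and 1178 days come from the SAP. The exposure-adjusted rates are unaffected, and so is any hypothesis test, since none is planned. This is a cheap improvement to the reporting of a descriptive study.

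**What to change.** In SAP 3.8.1, and for the TEAE tables in 3.8.7, state that the all-TEAE, non-serious, acute, severity and relationship percentages count events with onset from first dose to first dose+364, matching 3.8.4. Keep the SAE, AESI, death and discontinuation-AE tables over the full period. If a full-period all-TEAE table is also kept, add a footnote that non-serious capture is selective after year 1.

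The cost is a sentence or two of SAP text, a date filter, a footnote and a few extra tables, with no new data. The downsides are a somewhat lower headline TEAE percentage and that late events appear only in the full-period tables.

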3.8.2 Adverse Events of Special Interest

An Adverse Event of Special Interest (AESI) is one of scientific and medical concern specific to understanding of the investigational product. The AESIs will be summarized. AESIs for this protocol include:

- Hepatic Function Abnormality which are defined as any increase in alanine transaminase (ALT) or aspartate transaminase (AST) to greater than $3 \times$ upper limit of normal (ULN) and concurrent increase in bilirubin to greater than $2 \times$ ULN
- New or Reactivated Tuberculosis Infection
- Herpes Zoster Infection
- Malignancy
- Infusion, Hypersensitivity, and Anaphylactic Reactions
- Vasculitis

3.8.3 Deaths and Treatment Discontinuations due to Adverse Events

Deaths and AEs leading to treatment discontinuation will be summarized and listed.

3.8.4 Exposure Adjusted Adverse Events Rate

The exposure adjusted rate (per 100 patient-year) for treatment emergent AEs, non-serious AEs, acute AEs, investigational product related AEs, AEs by highest severity, AEs leading to treatment discontinuation, AEs resulting in death, SAEs and AESIs will be summarized. The exposure adjusted subject rate per 100 patient-years is defined as [the number of subjects with an event/(total exposure time in days/365.25)]*100.

For treatment emergent AEs leading to treatment discontinuation, AEs resulting in death, SAEs and AESIs, duration of exposure is calculated as follows:

- Anifrolumab Total group: duration of exposure (days) = minimum(end of study date in CD1145, last dosing date in CD1145+85 days) – first dosing date in CD1145+1.

- Anifrolumab 1000 mg group:
 - For subjects who received 1000 mg only during the study: duration of exposure (days) = minimum(end of study date in CD1145, last dosing date in CD1145+85 days) – first dosing date in CD1145+1.
 - For subjects who received both 1000 mg and 300 mg during the study: duration of exposure (days) = (first dosing date of 300 mg – 1) – first dosing date in CD1145 + 1.
- Anifrolumab 300 mg group: duration of exposure (days) = minimum(end of study date in CD1145, last dosing date in CD1145+85 days) – first dosing date of 300 mg +1.

The AEs leading to treatment discontinuation, AEs resulting in death, SAEs and AESIs occurred during the exposure period will be included in the summary.

The non-serious AEs are captured during the first year of subject's participation only. So for treatment emergent AEs, non-serious AEs, acute AEs, investigational product related AEs, and AEs by highest severity, duration of exposure is calculated as follows:

- Anifrolumab Total group: duration of exposure (days) = minimum(end of study date in CD1145, first dosing date in CD1145+364) – first dosing date in CD1145+1.
- Anifrolumab 1000 mg group:
 - For subjects who received 1000 mg only during the study: duration of exposure (days) = minimum(end of study date in CD1145, first dosing date in CD1145+364) – first dosing date in CD1145+1.
 - For subjects who received both 1000 mg and 300 mg during the study: duration of exposure (days) = minimum(first dosing date in CD1145+364, first dosing date of 300 mg-1) – first dosing date in CD1145 + 1.
- Anifrolumab 300 mg group: minimum(end of study date in CD1145, first dosing date in CD1145+364) - first dosing date of 300 mg +1.

The events occurred during the exposure period will be included in the summary.

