4.5.3 Treatment Regimen

Subjects will receive MEDI-546 300 mg administered as an IV infusion Q4W starting at Day 1 (Week 0) or the visit following approval of this amendment (for those subjects who

have already been dosed in this study) for up to 3 years or until the sponsor discontinues development of MEDI-546 for SLE, whichever comes first.

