7.3 Endpoints

7.3.1 Primary Endpoint

The primary objective of this study is to evaluate the long-term safety and tolerability of IV MEDI-546 in adult subjects with moderately-to-severely active SLE. The safety and tolerability of MEDI-546 will be assessed primarily by summarizing treatment-emergent AEs (TEAEs) and treatment-emergent SAEs (TESAEs). Other variables used for the safety assessments will include serum chemistry, hematology, urinalysis, vital signs, physical examination, ECG, and concomitant medications.

All TEAEs and TESAEs will be summarized by system organ class and preferred terms, by severity and relationship to investigational product. No formal statistical testing will be performed. Other safety variables as well as their changes from baseline (if applicable) will be summarized descriptively.

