2.2 Study Design

This is an open-label, multinational, multicenter study to evaluate the long-term safety and tolerability of anifrolumab in adult subjects with chronic, moderately-to-severely active SLE who were previously treated with investigational product (anifrolumab 300 mg, 1000 mg, or placebo) and completed study CD-IA-MEDI-546-1013 (CD1013) through treatment (48 weeks dosing) and follow-up (85 days) periods. The start of this OLE study (first dose) should occur within 28 days of the last visit of study CD1013 or at the discretion of the medical monitor if the start of this OLE study occurs outside the 28-day window.

Approximately 240 subjects will be enrolled to receive IV anifrolumab as a 1000 mg fixed dose administered over at least 30 minutes every 4 weeks starting at Day 1 (Week 0) for up to 3 years or until the sponsor discontinues development of anifrolumab for SLE, whichever

[REDACTED]

comes first. The dose was changed to 300 mg on 12Feb2015 (protocol amendment 4) as the efficacy and safety data from study CD1013 indicated that the 300 mg dose had a more favorable benefit:risk profile than the 1000 mg dose. All subjects will be followed for 85 days after receiving their last dose of anifrolumab.

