3.2.2 Treatment Groups for Analysis

Treatment group is Anifrolumab Total for all analyses except the exposure adjusted adverse event which will be summarized by Anifrolumab 300 mg, Anifrolumab 1000mg, and Anifrolumab Total.

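### For common adverse events the exposure-adjusted subject rate depends on window length, so if subjects switch dose within year 1, the dose and Total columns can differ at equal risk

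*SAP*

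**What the plan says.** SAP 3.8.4 gives one formula for every exposure-adjusted row: "The exposure adjusted subject rate per 100 patient-years is defined as [the number of subjects with an event/(total exposure time in days/365.25)]*100". Exposure is then defined in two blocks.

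- **Full-period block** (discontinuation AEs, deaths, SAEs, AESIs). Time runs to the end of study or to 85 days after the last dose, whichever is earlier.
- **First-year block** (any TEAE, non-serious, acute, drug-related, and by worst severity). Time is capped at 365 days from the first dose. For switchers the 1000 mg period ends at "minimum(first dosing date in CD1145+364, first dosing date of 300 mg-1"), and the 300 mg period runs from the first 300 mg dose to the same 365-day cap.

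On counting, the section adds "The events occurred during the exposure period will be included in the summary". No formula in either block ends at a subject's first event.

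SAP 3.2.2 reports all analyses for the Total group only, with one exception: the "exposure adjusted adverse event which will be summarized by Anifrolumab 300 mg, Anifrolumab 1000mg, and Anifrolumab Total". The dose periods arise because, in SAP 2.2, "The dose was changed to 300 mg on 12Feb2015 (protocol amendment 4"). Under Protocol 4.5.3 the 300 mg regimen applies "starting at Day 1 (Week 0) or the visit following approval of this amendment", the latter for subjects already dosed.

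**The concern.** A rate per patient-year is meant to allow comparison of groups followed for different lengths of time. This one does so only in part. A subject adds at most one to the numerator but keeps adding time to the denominator after the event, so a longer window lowers the rate when events are common.

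For a subject who switches within year 1, the two dose windows divide the Total window between them. The subject can count once in each dose column but only once in Total. Since this is the only AE summary split by dose, a reader of the any-TEAE or any-non-serious-AE row could take a difference in window length for a difference in risk.

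**Working it through.** The documents contain no AE rate to reproduce. Incidence, switch timing and the shares of subjects below are therefore assumptions. The windows are those of SAP 3.8.4.

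**Formulas.** With constant hazard λ and window T in years, the expected SAP rate is 100 × Σ(1 − exp(−λTᵢ)) / ΣTᵢ. The first-event rate is 100λ. For one-year incidence p and a complete first year, λ = −ln(1 − p) / (365/365.25). A switch on study day d gives T₁₀₀₀ = (d − 1)/365.25 and T₃₀₀ = (366 − d)/365.25. These sum to the Total window of 365/365.25.

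**Example at p = 80%.**

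- λ = 1.6094/0.99932 = 1.6105, so the first-event rate is 161.1 per 100 PY.
- Total column: 80/0.99932 = 80.1.
- All switch evenly over days 2 to 365: the mean window on each dose is 182.5 days (0.49966 years), and both dose columns read 100.7.
- Half on 1000 mg all year, half switching evenly: a switcher contributes on average 1.0071 × 0.49966 = 0.5032 subjects with an event on 1000 mg. The 1000 mg column is 100 × (0.5032 + 0.8)/(0.49966 + 0.99932) = 86.9. The 300 mg column stays at 100.7. The ratio is 100.71/86.94 = 1.158.

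**All four incidences, equal hazards throughout (rates per 100 PY).**

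| One-year incidence | 10% | 20% | 50% | 80% |
|---|---|---|---|---|
| First-event rate | 10.5 | 22.3 | 69.4 | 161.1 |
| SAP Total column | 10.0 | 20.0 | 50.0 | 80.1 |
| All switch evenly in year 1: each dose column | 10.2 | 20.8 | 55.8 | 100.7 |
| Same, 300/1000 ratio | 1.00 | 1.00 | 1.00 | 1.00 |
| Half on 1000 mg all year: 300/1000 ratio | 1.012 | 1.025 | 1.074 | 1.158 |
| Half on 300 mg from Day 1: 300/1000 ratio | 0.988 | 0.976 | 0.931 | 0.863 |

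Subjects on 1000 mg all year are given no 300 mg time. The SAP formula as written would not do this for someone who switches after day 365. A first 300 mg dose on study day 401 gives 364 − 400 + 1 = −35 days, because the formula has no floor at zero.

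**No switch within year 1.** At a hazard of 2 per year and equal windows, the 1000 mg, 300 mg and Total columns all read 86.5.

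**Full-period block.** The longest window is 156 × 7 + 85 + 1 = 1178 days (3.225 years). At 20% cumulative SAE incidence the Total column is 20/3.225 = 6.2, against a first-event rate of 6.9. The 300/1000 ratio is 1.00 with switches spread over days 29 to 1093, 0.93 if all fall in year 1, and 1.02 if all fall later. At a hazard of 0.05 per year with all switching at one year, the columns read 4.9, 4.7 and 4.6 (1000 mg, 300 mg, Total).

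**Effect of the change.** If time stops at the first event, expected time at risk is (1 − exp(−λT))/λ and every column returns 100λ. That result depends on a hazard that is constant and the same for all subjects. With gamma frailty of variance 1 in the half-on-1000-mg case, the ratio falls from 1.283 to 1.108 at 80% incidence and from 1.141 to 1.063 at 50%.

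**The case against.** The SAP defines its subject rate completely, and the rate is a valid description of the data. Dose comparison is not an objective, and Protocol 7.3.1 says "No formal statistical testing will be performed". In switchers 300 mg always follows 1000 mg, so no denominator yields a clean dose contrast. Under moderate assumptions the dose ratio is close to 1, and the proposed denominator looks perfect only because the model assumes constant, equal hazards. All of this stands, and it limits the weight of the point. It does not remove it: the table still prints dose columns side by side as rates.

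Three stronger readings are tempting but not supported.

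- *The columns always differ.* In the first-year block the gap between dose and Total at equal risk requires switches within year 1 or otherwise unequal windows. The documents do not say how many subjects switched in that year.
- *The first-year Total merely repeats the percentage in SAP 3.8.1.* That section says "Specific adverse events will be counted once for each subject for calculating percentages" but states no one-year window, and Protocol 6.1.1 captures SAEs and AESIs throughout participation. The two figures need not coincide.
- *The formula favours one dose.* The direction depends on the mix of window lengths: the assumed cases give ratios on both sides of 1.

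**Conclusion.** The point holds in a limited form. For common first-year categories, the SAP rate can show differences between the dose columns, and between dose and Total, when hazards are equal. This requires some subjects to switch within year 1.

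In the assumed mixed cases the 300/1000 ratio is within about 2.5% of 1 at incidences up to 20%, about 7% away at 50%, and 14% to 16% away at 80%. If all switch evenly, the dose columns agree but exceed the Total by 100.71/80.05 = 1.26 at 80% incidence and 55.78/50.03 = 1.11 at 50%. These figures rest on constant hazard, a complete first year and assumed switch patterns, so the actual size and direction are unknown.

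The effect is small for rare AESIs. It is also small for discontinuation AEs, where time after dosing stops is at most 85 days. It is absent for deaths, where follow-up ends at the event. This is a worthwhile improvement to a descriptive table; it does not undermine the safety analysis.

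**What to change.** In SAP 3.8.4:

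1. Define the denominator for each event category as the sum over subjects of time from the start of that column's exposure period to the first event of the category within the period, or to the end of the period if there is none.
2. For rows by worst severity, stop time at the first event of the severity level being counted.
3. In the first-year 300 mg column, include only subjects whose first 300 mg dose falls no later than 364 days after their first dose in this study, so that no negative time enters.
4. State with the table that dose and period remain confounded in switchers.

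If the present formula is kept, add a note that for common categories the dose and Total columns are not directly comparable.

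The cost is a short SAP edit and minor programming. Onset dates are already needed to place events in exposure periods. The stated rates for common events will be higher (161.1 instead of 80.1 per 100 PY in the 80% example). Window dependence is reduced but not removed when risk varies between subjects.
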